This study assesses the primary efficacy endpoint at 3 weeks because it is clinically relevant as a timeframe within which demonstrated efficacy of a drug for ICP will be important for clinical decision making. In a large population-based, case-control study (Geenes et al. 2014), 669 patients with a singleton pregnancy were identified within the UK Obstetric Surveillance System (UKOSS) as having severe ICP; the mean gestational age was 33 weeks 4 days at time of diagnosis in these patients. Additionally, in a recent double-blind, multicenter, randomized placebo-controlled study that enrolled 605 women with ICP in the United Kingdom (Chappell et al. 2019), the median gestational age was 34.4 weeks at randomization. With the mean/median gestational ages at diagnosis occurring between 33 and 34 weeks—and with Royal College of Obstetricians and Gynaecologists (RCOG) guidelines (2011) recommending consideration of elective delivery for patients with ICP after 37 weeks based on sBA-related risks of stillbirth—approximately 3 weeks of study drug treatment corresponds to a timeframe within which demonstration of sBA reduction is expected to be impactful for clinical decision making. Furthermore, based on clinical experience with another IBAT inhibitor (maralixibat),

continued improvements in sBA are likely to be seen with relatively longer treatment durations, arguing against analysis of sBA prior to the 3-week timeframe as a primary efficacy endpoint. In Study LUM001-501, decreases in both sBA and ItchRO (observer) were observed at Week 2 and continued to decline even further at Week 4 in pediatric participants with non-truncating PFIC2, supporting the benefit of treatment durations >2 weeks for reduction of sBA and pruritus. However, given the mean/median gestational ages for ICP diagnosis (33–34 weeks), along with the requirement for randomization no later than 36 weeks 0 days in Part 2, participants are relatively more likely to be at the upper range of gestational age eligibility in this study, and as such, relatively few participants in this study will be expected to remain on treatment beyond 3 weeks.

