#### 10.4.1.4. Exploratory Efficacy Endpoints

The exploratory efficacy endpoints are defined in [Section 3.4](#). The change in total sBA from Week 3 (primary endpoint) to delivery will be considered, and the difference between treatment groups will be tested using a randomization-based version of rank analysis of covariance (ANCOVA; [Stokes et al. 2012](#)). In a similar manner, the change from baseline in total sBA concentration to the time of delivery will also be explored. An additional analysis will be performed that examines the change from baseline to delivery but that averages across the last 2 time points on or prior to delivery. Similar analyses will be performed for Adult ItchRO. Associations between the changes from baseline to Week 3 in total sBA and Adult ItchRO will be assessed using either Pearson’s or Spearman’s correlation coefficient. “Responder” analyses for composite perinatal outcomes will be performed using baseline sBA and ItchRO and the change at Week 3 values in sBA and ItchRO as covariates and, separately, using the Week 3 values themselves (instead of the change at Week 3).

Change in biomarkers of bile acid synthesis, inflammation, and pruritogens as well as the proportion of participants with sBA <40 µmol/L at the end of the treatment period will also be explored. The change in biomarkers will follow the same approach as other exploratory efficacy endpoints described above. The proportion of participants with sBA <40 µmol/L at the end of the treatment period will be analyzed in the same manner as the secondary efficacy endpoint for composite perinatal outcomes.

Further exploratory efficacy endpoints include continuous and binary endpoints on additional perinatal outcomes. The analysis of continuous endpoints will follow the same approach as other exploratory efficacy endpoints described above. Binary outcomes will be analyzed in the same manner as the secondary efficacy endpoint for composite perinatal outcomes. Additional details will be included within the SAP.

The secondary endpoint of composite perinatal outcomes will also be explored using an ordinal scale, with ranks assigned according to the severity of the outcomes specified within [Section 3.2](#).

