### **1.1.4. Exploratory Objectives and Endpoints**

The following exploratory objectives and endpoints are applicable to both the primary and open-label supplemental cohorts:

- To assess volixibat drug levels in maternal and fetal plasma and pharmacodynamic (PD) markers in maternal blood in participants with ICP on the basis of the following endpoints:

- Volixibat concentrations in maternal and fetal plasma (from umbilical cord sampling)  
Note: Assessment of maternal/fetal volixibat drug levels is a secondary objective for the open-label supplemental cohort.
- Change in biomarkers of bile acid synthesis, inflammation, and pruritogens
- Proportion of participants with sBA <40  $\mu\text{mol/L}$  at end of the treatment period
- To assess the longer-term efficacy of volixibat in participants with ICP on the basis of the following endpoints:
  - Mean change from Week 3 to end of study treatment period in total sBA concentration
  - Mean change from baseline to end of study treatment period in total sBA concentration
  - Association between changes from baseline to Week 3 in total sBA and ItchRO as well as their association with the composite perinatal outcome
- To assess the effect of volixibat on additional perinatal outcomes on the basis of the following endpoints:
  - Mean gestational age at delivery
  - Proportion of participants with an early term delivery (37–38 weeks 6 days, inclusive)
  - Proportion of participants with a full-term delivery ( $\geq 39$  weeks)
  - Proportion of participants experiencing a perinatal death
  - Proportion of participants with a spontaneous preterm delivery
  - Proportion of participants with an iatrogenic preterm delivery attributable to ICP
  - Proportion of neonates requiring neonatal intensive care unit (NICU) admission for  $\geq 12$  hours between birth and hospital discharge
  - Proportion of neonates with meconium-stained amniotic fluid at delivery
  - Proportion of participants requiring rescue medication for ICP
  - Proportion of neonates with Apgar score <7 at 5 minutes of life
  - Mean birth weight percentile
  - Mean placental weight percentile
  - Proportion of neonates with umbilical cord pH <7.0 at birth
  - Means for umbilical cord blood sBA, total cholesterol, LDL cholesterol, and glucose
  - Mean maternal estimated blood loss at delivery
  - Mean time from randomization to delivery

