### 3.8.2. Analysis Visit Windows

Participant visits might not occur on protocol-specified days. Therefore, for the purpose of analysis, observations will be assigned to analysis windows. A notable exception to the analysis visit windows below is the end of treatment/date of delivery. This will be summarized as its own visit and that will be the value used for endpoints that look at either the value or change from baseline to delivery.

The analysis windows for ItchRO, sBA, hematology, chemistry, coagulation, weight, vital Signs, and urinalysis are provided in [Table 2](#).

The analysis windows for 5-D Itch, EQ-5D-5L, PROMIS Fatigue and Sleep patient reported outcomes (PROs), PIS-Itch, PGIC-Itch, and Biomarker samples (7 $\alpha$ -hydroxy-cholesten-3-one [7 $\alpha$ C4], fibroblast growth factor 19 [FGF-19], autotaxin, progesterone sulfate, and glucagon-like peptide 1 [GLP-1]) are provided in [Table 3](#).

The analysis windows for lipid panel and glycated albumin are provided in [Table 4](#).

The analysis windows for vitamin A, D, and E levels and fetal ultrasound are provided in [Table 5](#).

**Table 2 Analysis Visit Windows for ItchRO^, sBA, Hematology\*, Chemistry\*, Coagulation\*, Weight, Vital Signs, and Urinalysis**

Nominal Visit	Nominal Study Day	Lower Limit	Upper Limit
Baseline	1	(none)	1
Week 1	8	2	11
Week K (K is every week after previous visit)	K*7 + 1	K*7 – 2	K*7 + 4

^ ItchRO is collected daily, but will have weekly averages calculated and results will be grouped according to the analysis windows above.

\* Hematology, chemistry, and coagulation are not planned to be collected at the baseline visit. Rather, the screening visit (or a subsequent unscheduled visit) will serve as the baseline.

**Table 3 Analysis Visit Windows for 5-D Itch, CSS, EQ-5D-5L, PROMIS Fatigue and Sleep PROs, PIS-Itch, PGIC-Itch, and Biomarker Samples (C4, FGF-19, Autotaxin, Progesterone Sulfate, GLP-1)**

Nominal Visit	Nominal Study Day	Lower Limit	Upper Limit
Baseline*	1	(none)	1
Week 3	22	19	25

\*PGIC-Itch was not collected at baseline.

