### 3.8.3. Selection of Data in the Event of Multiple Records in an Analysis Visit Window

Depending on the statistical analysis method, single values may be required for each analysis window. For example, change from baseline by visit usually requires a single value, whereas a time-to-event analysis would not require 1 value per analysis window.

If multiple valid, nonmissing, continuous measurements exist in an analysis window, records will be chosen based on the following rules if a single value is needed:

- In general, the baseline value will be the last nonmissing value on or prior to the first dose of study drug, unless specified differently. If multiple measurements occur on the same day, the last nonmissing value prior to the time of first dose of study drug will be considered as the baseline value. If these multiple measurements occur at the same time or the time is not available, the average of these measurements (for continuous data) will be considered the baseline value.

- For postbaseline values:
  - The record closest to the nominal day for that visit will be selected.
  - If there are 2 records that are equidistant from the nominal day, the later record will be selected.
  - If there is more than 1 record on the selected day, the average will be taken, unless otherwise specified.
  - If a participant gives birth prior to Week 3, then the value obtained at the date of delivery will be analyzed according to the next analysis window after the previous visit. For example, if there was a Week 2 sample provided on Day 15 and then the participant delivered on Day 18, the Day 18 record would be mapped to Week 3, even though it is contained within the upper bound of the Week 2 analysis window. This is designed to minimize the amount of missing data for the primary endpoint.

If multiple valid, nonmissing, categorical measurements exist in an analysis window, records will be chosen based on the following rules if a single value is needed:

- For baseline, the last available record on or prior to the date of the first dose of study drug will be selected. If there are multiple records with the same time or no time recorded on the same day, the value with the lowest severity will be selected (e.g., normal will be selected over abnormal for safety electrocardiogram [ECG] findings).

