“Responder” analyses for composite perinatal outcomes will be performed using baseline sBA and ItchRO and the change at Week 3 values in sBA and ItchRO as covariates and, separately, using the Week 3 values themselves (instead of the change at Week 3).

The change in total sBA from Week 3 (primary endpoint) to delivery will be considered, and the difference between treatment groups will be tested using a randomization-based version of rank analysis of covariance (ANCOVA) (Stokes et al. 2012). In a similar manner, the change from baseline in total sBA concentration to the time of delivery will also be explored. An additional analysis will be performed that examines the change from baseline to delivery but that averages across the last two time points on or prior to delivery. Similar analyses will be performed for Adult ItchRO. Associations between the changes from baseline to Week 3 in total sBA and Adult ItchRO will be assessed using Pearson’s and Spearman’s correlation coefficient. Additionally, a scatterplot of two variables will also be produced.

The following endpoints will be summarized by treatment arm and the summary statistics by treatment arm and the treatment differences will be tabulated:

- Mean gestational age at delivery
- Mean birth weight percentile
- Mean placental weight percentile
- Means for umbilical cord blood sBA, total cholesterol, LDL cholesterol, and glucose
- Mean maternal estimated blood loss at delivery
- Mean time from randomization to delivery

Further exploratory efficacy endpoints include continuous and binary endpoints on additional perinatal outcomes. The analysis of continuous endpoints will follow the same approach as other exploratory efficacy endpoints. Binary outcomes will be analyzed in the same manner as the secondary efficacy endpoint for composite perinatal outcomes.

The secondary endpoint of composite perinatal outcomes will also be explored using an ordinal scale, with ranks assigned according to the severity of the outcomes specified within [Section 3.2](#).

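### A participant who delivers after her Week 2 visit but before Week 3 gets a Week 3-to-delivery sBA change of zero by construction, because one delivery record supplies both values

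*SAP*

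**What the plan says.** Among the longer-term efficacy endpoints, SAP 1.1.4 lists "Mean change from Week 3 to end of study treatment period in total sBA concentration". SAP 1.2 ends the treatment period on the day of delivery. SAP 6.3 says "The change in total sBA from Week 3 (primary endpoint) to delivery will be considered", and tests this change between arms with a randomization-based rank analysis of covariance; Protocol 10.4.1.4 plans the same.

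Two data-handling rules supply the two values:

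- **Delivery value.** SAP 3.8.2 treats delivery as a visit of its own, outside the ordinary windows, and says "that will be the value used for endpoints that look at either the value or change from baseline to delivery".
- **Week 3 value after an early birth.** For a participant who gives birth before Week 3, SAP 3.8.3 says "the value obtained at the date of delivery will be analyzed according to the next analysis window after the previous visit". Its example has a Week 2 sample on Day 15 and a delivery on Day 18, and concludes that "the Day 18 record would be mapped to Week 3". The stated reason is to limit missing data for the primary endpoint.

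SAP 6.3 does not restrict the Week 3-to-delivery analysis to participants with a separate Week 3 sample, and does not say how early deliverers are handled.

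**The concern.** The mapping rule was written for one purpose, filling the Week 3 cell of the primary analysis, but nothing confines it to that purpose. SAP 6.3 ties its Week 3 value to the primary endpoint, so on a literal reading the mapped value carries over. The delivery record is then both the start and the end of the interval being measured.

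A change of zero reads as an effect fully maintained after Week 3. These participants have no time after Week 3, so they carry no information on durability. Including them pulls the mean difference toward zero and adds a block of ties at zero to the rank analysis.

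The share of zeros may also depend on treatment. Protocol 8.1.12 links advice on delivery timing to bile acid level. Protocol 8.2.3 lists persistently elevated or rising sBA among the indications for iatrogenic preterm delivery. A drug that lowers sBA could therefore change how many participants in each arm deliver between the Week 2 and Week 3 visits.

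**Working it through.** **Inputs.** SAP Table 2 puts Week K at nominal Day 7K + 1, with limits 7K − 2 to 7K + 4. SAP 3.8.1 makes Day 1 the day of first dose. I assume visits on schedule at Days 8 and 15 and read *before Week 3* as before nominal Day 22.

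**Step 1: reproduce the SAP's example.**
- Week 2 window: 7×2 − 2 = 12 to 7×2 + 4 = 18.
- Week 3 window: 7×3 − 2 = 19 to 7×3 + 4 = 25.

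Day 18 falls in Week 2 by window. The previous visit was Week 2, so the early-delivery rule sends the record to Week 3, as the SAP states.

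**Step 2: score the example under SAP 6.3.** Change = delivery value − Week 3 value = Day 18 record − Day 18 record = 0. If several samples are drawn that day, SAP 3.8.3 averages them, and the same average fills both roles.

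**Step 3: apply the rule to every early delivery day.**

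| Delivery day | Last visit | Record mapped to | Week 3 value | Week 3-to-delivery change |
|---|---|---|---|---|
| 2–8 | none after baseline | Week 1 | none | missing |
| 9–15 | Week 1 | Week 2 | none | missing |
| 16–21 | Week 2 | Week 3 | the delivery record | 0 |

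Off-schedule visits shift these ranges. A participant who missed Week 2 and delivers before Week 3 is mapped to Week 2 and is also missing. SAP 3.6.1 imputes nothing unless a method is given, and none is given here.

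**Step 4: effect on the mean difference.** Let z be the share of analysed participants in each arm with a structural zero, and D the between-arm difference among those with a real interval. The expected difference is (1 − z)·D + z·0 = (1 − z)·D.

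| Assumed z | Multiple of D |
|---|---|
| 5% | 0.95 |
| 10% | 0.90 |
| 20% | 0.80 |

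**Step 5: unequal shares with no drug effect after Week 3.** Suppose the true change is −10 µmol/L in both arms, with zeros in 12% of placebo and 8% of volixibat participants (all assumed). Placebo mean = 0.88 × (−10) = −8.8. Volixibat mean = 0.92 × (−10) = −9.2. Spurious difference = −9.2 − (−8.8) = −0.4 µmol/L.

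**Step 6: effect on power.** A simulation used 4,000 replicates, 100 analysed per arm, a true difference of 10 and SD 25. Power with zeros included against power in participants with two distinct samples was 76.2% against 76.8% at 5% zeros, and 72.9% against 73.8% at 10%. It used an unadjusted Mann-Whitney test, not the planned rank analysis of covariance, so it gives only the order of size.

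**The case against.** The strongest reply is that intent is visible and little depends on the result. The mapping is justified only by the primary endpoint, so a careful programmer might not carry it over. The endpoint is exploratory, is not in the hierarchy of SAP 3.5, and decides no success criterion. Protocol 10.4.1.1 expects few deliveries before Week 3, and at small shares the loss of power is about a percentage point or less. All of this stands as a limit on importance. It does not remove the defect: the written rules give a zero in the SAP's own example, and no sentence switches the mapping off.

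A reader might also infer more than the documents support:

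- **That everyone who delivers before Week 3 scores zero.** Only those whose last visit was Week 2 do; the rest are missing.
- **That no other between-arm test looks past Week 3.** SAP 6.3 also tests baseline-to-delivery change and the proportion with sBA below 40 µmol/L at end of treatment. Neither subtracts a Week 3 value.
- **That the supportive analysis which "averages across the last 2 time points on or prior to delivery" counts one record twice.** That analysis runs from baseline to delivery. In the SAP's example its two time points are naturally Day 15 and Day 18, and relabelling a record does not create another time point.
- **That ItchRO has the same fault.** It is a daily diary analysed as weekly averages, and the SAP does not say how a single-record delivery rule would act on them.
- **That the affected share must be large.** Protocol 4.3.2.1 says "relatively few participants in this study will be expected to remain on treatment beyond 3 weeks", which sits uneasily with the expectation of few early deliveries, but neither statement gives a rate. A delivery on Day 24 after a Week 3 visit leaves two real samples, and a delivery on Day 10 leaves a missing change. Only the interval between the Week 2 and Week 3 visits produces zeros.

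**Conclusion.** The concern holds in this limited form: the zero and missing patterns follow from the written rules, with the exact day ranges depending on on-schedule visits. The loss in the mean difference equals the share of zeros when that share is the same in both arms. Since the documents give no rate, the effect may be small. Bias from unequal shares is possible, because delivery timing is partly guided by sBA, but its size cannot be set from the documents. The primary analysis and the confirmatory claims are untouched by this point. It still merits correction, because a stated rule yields a value that measures no change and the remedy is short.

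**What to change.** Add to SAP 3.8.3 that the early-delivery mapping does not apply to the Week 3-to-delivery endpoint. Add to SAP 6.3 that this endpoint is analysed only in participants with a Week 3 sample distinct from, and earlier than, the delivery record; that N is reported per arm; and that the result is descriptive, because the subset is selected after randomization.

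Both statements are needed. A delivery record from Days 19 to 21 already lies inside the Table 2 Week 3 window, so switching off the mapping alone could leave room to reuse it; the distinct-sample condition closes that gap.

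The cost is a few sentences and a smaller N for one exploratory endpoint. The mapping can stay as written for the primary endpoint as far as this point goes.

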**Table 6 Perinatal Outcome Severity Scoring**

Perinatal Outcome	Score
Perinatal death	4
Spontaneous preterm delivery	3
Iatrogenic preterm delivery attribute to ICP or ICP-related complications	2
Neonatal unit admission for $\geq 12$ hours from birth until hospital discharge for any of the reasons listed in Section 1.1.3	1
No perinatal outcome	0

The score is assigned according to the most severe outcome following the order shown above. If a participant experiences perinatal death, spontaneous preterm delivery, or iatrogenic preterm delivery attributed to ICP or ICP-related complications AND neonatal unit admission for  $\geq 12$  hours from birth until hospital discharge for any of the reasons listed in [Section 3.2](#), the score will be adjusted by 0.5. For example, if a participant has spontaneous preterm delivery followed by a neonatal unit admission, the score would be  $3+0.5=3.5$ , where the 3 comes from the spontaneous preterm delivery and the 0.5 comes from the fact that neonatal unit admission occurred. This will be analyzed using a stratified log rank test that provides more weight to the more severe outcomes and will employ a randomization-based covariance adjustment ([Zink and Koch 2012](#)).

Change in biomarkers of bile acid synthesis, inflammation, and pruritogens as well as the proportion of participants with sBA  $<40$   $\mu\text{mol/L}$  at the end of the treatment period will also be explored. The change in biomarkers will follow the same approach as other exploratory efficacy endpoints described above. The proportion of participants with sBA  $<40$   $\mu\text{mol/L}$  at the end of the treatment period will be analyzed in the same manner as the secondary efficacy endpoint for composite perinatal outcomes.

## **7. SAFETY ANALYSES**

Safety summaries will be separated by the portion of the study in which they occurred. There are two parts of the double-blind part of the study and the open-label supplemental cohort.

### **7.1. Adverse Events and Deaths**

Adverse events are captured both for the participant (mother) and their child. As a result, summaries and listings will be presented separately.

#### **7.1.1. Adverse Event Dictionary**

Clinical and laboratory AEs will be coded using the MedDRA version 23.1. System organ class (SOC), high-level group term (HLGT), high-level term (HLT), preferred term (PT), and lower-level term (LLT) will be provided in the AE dataset.

